**Hypothesis 1.2:  $PTSD_{sev}$  will strongly correlate with PTSD symptom severity level**

Using the same database as in retrospective study and focusing only on PTSD subjects, an analogous approach to that described for hypothesis 1.1 will be used. The principal difference will be that the independent variable,  $PTSD_{sev}$ , is a continuous variable rather than a categorical variable. Therefore, multiple linear regression will be used with  $PTSD_{sev}$  as the independent variable, and the PCL-5 symptom severity scale as the dependent variable acquired on the day of the sleep study. We will also examine the correlation of  $PTSD_{sev}$  with the other measures of quality of health and life in the database, particularly RQP (Rivermead Post-Concussive Symptom Questionnaire), PHQ-9 (Patient Health Questionnaire), FOSQ (Functional Outcome of Sleep Quality), ISI (Insomnia Severity Index), and Promis-29. The results of these analyses will provide a comprehensive examination of this hypothesis with respect to how accurately  $PTSD_{sev}$  can determine the severity of PTSD, and how well it is correlated with quality of life measures.

**Hypothesis 2: Use of a dense array (up to 64 channel) EEG montage, as compared to 6-channel EEG, will improve discrimination of PTSD patients from control subjects without PTSD.**

For this analysis, the most promising  $PTSD_{dx}$  neuromarker identified in Hypothesis 1.1 (phase 2 development and validation analysis) will be prospectively evaluated in up to 25 PTSD and control subjects. First, a standardized effect size (mean difference / standard deviation) and corresponding 95% confidence interval will be calculated for the  $PTSD_{dx}$  neuromarker using the conventional 6- channel EEG approach. Then, using forward stepwise linear regression, extra EEG electrodes whose addition increases the model coefficient of determination ( $R^2$ ) by at least 1% will be included as candidate extra EEG channels. Once a final model is fit (with  $>6$  electrodes), the corresponding standardized effect size and 95% confidence interval will be calculated. Given the pilot nature and sample size for this analysis ( $n=25$ ), interpretation will not be based on formal statistical testing, but rather on the difference in the two effects sizes generated from the 6-channel EEG analysis vs. the  $>6$ -channel EEG analysis. Given that effect sizes can be interpreted as “small” (0.2), “medium” (0.5), or “large” ( $\geq 0.8$ ), we will use half of the width of adjacent categories (i.e. 0.15) to interpret meaningful improvement with the use of more than 6 EEG channels. For example, if the standardized effect size for the 6-channel EEG was 0.70, the  $>6$ -

channel EEG effect size would need to be  $\geq 0.85$  to indicate meaningful improvement and potential indication for a more complex EEG testing approach.

**Hypothesis 3:  $PTSD_{sev}$  will strongly correlate with the changes of PTSD symptoms and other measures of Quality of Health and Life as a result of psychotherapy.**

For this analysis, change in  $PTSD_{sev}$  identified from Aim 1 is the primary independent variable of interest and change in CAPS-5, PCL-5, BDI-II, Q-LES-Q-SF, and PSQI serve as dependent variables. Since the CAPS-5 will be administered at only 2 time-intervals, multiple linear regression analysis will be used adjusting for baseline CAPS-5 score and CAPS-5 score after treatment as the dependent variable. For the PCL-5, BDI-II, Q-LES-Q-SF, and PSQI there will be 4 outcome measurements corresponding to pre-treatment, within one week after the initiation of therapy, at the completion of treatment, and at three-months post therapy. For these measures, linear mixed models will be used to examine the strength of association between the slope (change) for  $PTSD_{sev}$  and the slope for the dependent variables (evaluated in separate models). To assess if the rate of change is curvilinear, a quadratic parameter will be tested. Due to multiple

observations per subject, an autoregressive correlation structure will be specified to account for within-subject correlation. Also, given 5 outcome variables of interest, a “corrected” p-value of <0.01 will be used to define statistical significance.

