### 3.2 Type of Study

This project consists of three type of studies:

Study 1. This is a retrospective study. At ENRM VA, the Neuromarker analyses will be applied to a large existing database (n=656) containing sleep EEG recordings along with health and functional outcome measures, from Veterans with PTSD only (n=107), TBI only (n=126), both PTSD and TBI (n=87), depression only (n=80), and controls (no PTSD/TBI/Depression; n=256).

Study 2. This is a prospective pilot study at ENRM VA that will be conducted to evaluate potential improvement on the performance of the Neuromarkers using a dense array (up to 64 channels) EEG montage that covers all areas of the brain and with greater resolution, as compared to the original 6-channel EEG protocol. The sample will include up to 25 PTSD and control subjects.

Study 3. This is a prospective study conducted at ENRM VA on a single cohort of up to 55 Veterans with PTSD at multiple times during their ongoing clinical treatment for PTSD at the ENRM VA. Night time sleep EEG measures will be collected at pre-treatment, after first session of therapy, immediately after completion of therapy, and at 3-month post therapy. Measures of PTSD symptom severity, as well as measures of health and functional outcomes will be collected at the beginning and completion of therapy.

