### 3.5 Analysis Plan

#### **Hypothesis 1.1 $PTSD_{dx}$ will discriminate PTSD patients from control subjects without PTSD;**

The primary evaluations will be based on computation of  $PTSD_{dx}$  and  $PTSD_{sev}$  markers similar to the approach used in preliminary studies. This will occur in multiple phases, all of which will randomly divide and analyze the full sample of 656 veterans into 3 groups of 219, 219, and 218 subjects, and in proportion to the presenting symptom/condition status of veterans, as follows:

Condition (Group)	Total N	Subsample		
		Sample 1	Sample 2	Sample 3
PTSD only (group A)	107	36	36	35
TBI only (group B)	126	42	42	42
PTSD & TBI (group C)	87	29	29	29
Depression only (group D)	80	26	27	27
Controls (no PTSD, TBI, depression) (group E)	256	86	85	85

To test our first hypothesis and in the first phase of analysis, we will use the specific  $PTSD_{dx}$  neuromarker previously identified in our preliminary study of 76 veterans, and evaluate it separately in all 3 subsamples. Analysis of covariance (ANCOVA) will be used to compare adjusted mean  $PTSD_{dx}$  scores between the PTSD only group (Group A) vs. planned contrasts with the remaining 4 groups. The a-priori-defined contrasts will consist of the following 5 comparisons: A vs. E, A vs. B/C/D combined, A vs. B, A vs. C, and A vs. D. Thus, for each subsample, there will be 5 planned comparisons, and hence a total of 15 comparisons. We expect the largest differences in mean  $PTSD_{dx}$  scores between PTSD only (group A) and controls (Group E), but nonetheless, also expect the PTSD only group to have higher mean  $PTSD_{dx}$  scores than Groups B, C, and D.

In these analyses, models will be adjusted for potential confounding variables (e.g. current use of sleep medications) identified by use of student *t*-tests (or Wilcoxon tests) for continuous variables and chi-square tests for categorical variables. Given the 5 planned comparisons for each subsample, a modified p-value of 0.01 will be used to define statistical significance. While arbitrary, “validation” of the previously identified  $PTSD_{dx}$  neuromarker will be based on statistical significance as follows: (i) all 3 comparisons of Group A vs. Group B at  $p<0.01$ , AND at least 9 of the 12 remaining comparisons at  $p<0.01$ .

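### Hypothesis 1.2 would test the preliminary PTSD_sev marker in random thirds of the PTSD records with no pooled analysis, which adds no validation and loses power and precision

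*Combined protocol and SAP*

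**What the plan says.** Section 3.5 opens Hypothesis 1.1 by naming both markers, PTSD_dx and PTSD_sev, and describes several phases, "all of which will randomly divide and analyze the full sample of 656 veterans into 3 groups of 219, 219, and 218 subjects". In phase 1 the plan takes the PTSD_dx "neuromarker previously identified in our preliminary study of 76 veterans" and will "evaluate it separately in all 3 subsamples". In phase 2 a marker is re-selected in Subsamples 1 and 2 and tested in Subsample 3.

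Hypothesis 1.2 then says that, among PTSD subjects only, "an analogous approach to that described for hypothesis 1.1 will be used". The main difference it names is that the predictor is continuous, so PCL-5 is regressed on PTSD_sev by multiple linear regression. Correlations with several other health and quality-of-life measures are to be examined as well.

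The Hypothesis 1.2 text gives no sample size, significance level or success rule. It does not say which groups count as PTSD subjects, or whether PTSD_sev is carried over from the preliminary work or re-selected. No pooled analysis is described. Section 2.2 reports that a PTSD severity marker already exists from the preliminary studies.

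**The concern.** The two phases of Hypothesis 1.1 use the split for different purposes. In phase 2 it is needed, because a marker chosen on some records must be tested on others. In phase 1 the marker comes from earlier work, so nothing has to be trained.

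For a marker fixed in advance, random thirds of one database are not three independent validations. They come from the same sleep laboratory and the same referral route, so agreement among them says nothing about transfer to another setting that a single pooled estimate would not say. Each third simply has a third of the records.

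The stake is the headline answer to Hypothesis 1.2. Its aim is to show how strongly the marker tracks severity and how accurately it measures it, which is largely a question of estimation. Three wide intervals, possibly discordant and with no stated way of combining them, answer that less well than one narrower interval from the same data.

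**Working it through.** **Counts.** The subsample table under Hypothesis 1.1 reads "PTSD only (group A) 107 36 36 35" and "PTSD & TBI (group C) 87 29 29 29". The totals agree with section 3.2: "Veterans with PTSD only (n=107), TBI only (n=126), both PTSD and TBI (n=87".
- All five groups per subsample: 36+42+29+26+86 = 219; 36+42+29+27+85 = 219; 35+42+29+27+85 = 218. The plan's own sizes are reproduced.
- Groups A and C: 36+29 = 65, 36+29 = 65, 35+29 = 64; total 107+87 = 194.
- Group A alone: 36, 36 and 35; total 107.

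**Assumptions.** The plan gives no target correlation and no alpha for Hypothesis 1.2. I therefore took true correlations r from 0.2 to 0.5 and two-sided alpha of 0.01 (the Hypothesis 1.1 level) and 0.05. Covariates are ignored.

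**Power.** By the Fisher z approximation, power = Φ(√(n−3)·atanh(r) − z), with z = 2.576 at alpha 0.01 and 1.960 at alpha 0.05. The opposite tail is negligible.

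For r = 0.30, atanh(r) = 0.3095:
- n = 65: √62 = 7.874 and 7.874 × 0.3095 = 2.437. Alpha 0.01: Φ(−0.139) = 0.445. Alpha 0.05: Φ(0.477) = 0.683.
- n = 194: √191 = 13.820 and 13.820 × 0.3095 = 4.278. Alpha 0.01: Φ(1.702) = 0.956. Alpha 0.05: Φ(2.318) = 0.990.

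| True r | One third (65), alpha 0.01 | All 194, alpha 0.01 | One third (65), alpha 0.05 | All 194, alpha 0.05 |
|---|---|---|---|---|
| 0.2 | 16% | 59% | 36% | 80% |
| 0.3 | 45% | 96% | 68% | 99% |
| 0.4 | 78% | 99.9% | 92% | >99.9% |
| 0.5 | 96% | >99.9% | 99% | >99.9% |

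With Group A only, power at r = 0.30 in a third of 36 against all 107 is 21% vs 72% at alpha 0.01, and 43% vs 88% at alpha 0.05.

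**Detectable correlation.** For 80% power at alpha 0.01, r = tanh((2.576 + 0.842)/√(n−3)). This is tanh(0.434) = 0.41 for n = 65 and tanh(0.247) = 0.24 for n = 194.

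**Precision.** The 95% interval is tanh(atanh(r) ± 1.96/√(n−3)). At an observed r = 0.5, atanh(r) = 0.5493:
- n = 65: 0.5493 ± 0.2489, giving 0.29 to 0.66 (width 0.37).
- n = 194: 0.5493 ± 0.1418, giving 0.39 to 0.60 (width 0.21).

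**The case against.** The best defence is that the Hypothesis 1.2 text is thin and that the split enters it only by reference. Four limits follow, and all of them stand.

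- **Fixed or re-selected.** A reader might infer that PTSD_sev is fixed throughout Hypothesis 1.2. The documents do not support that. The marker that phase 1 explicitly carries over is PTSD_dx, and Hypothesis 3 refers to PTSD_sev as coming out of Aim 1, which suggests re-selection. The point therefore applies to the phase 1 analogue only. In a phase 2 analogue the training and validation split is right.
- **The 0.01 level.** A reader might infer that 0.01 carries over and has no basis here, because Hypothesis 1.1 derives it from five group contrasts. The text sets no level for Hypothesis 1.2. A strict level could also be defended by the several other measures listed beside PCL-5, and Hypothesis 3 uses 0.01 because it has five outcomes. The loss from splitting appears at 0.05 as well.
- **A requirement to succeed in every third.** No such rule is stated for Hypothesis 1.2. Purely as illustration, at alpha 0.01 the chance of significance in all three thirds would be about 9% at r = 0.30 and 46% at r = 0.40. Under an equally hypothetical two-of-three rule it would be about 42% and 87%. Neither pair measures the plan's actual power.
- **The denominator.** PTSD subjects are not defined here. In Hypothesis 1.1 Group C is a comparator, so 194 is an assumption. The Group A figures show the same pattern.

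The hypothesis also predicts a strong correlation, and for a strong one power in a single third is already high. That confines the power argument to weak and moderate correlations. It does not answer the precision argument.

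**Conclusion.** The concern holds for the preliminary PTSD_sev marker. The opening of the analysis plan names that marker and applies the split to all phases, Hypothesis 1.2 adopts the approach by analogy, and no pooled analysis is given. Splitting then adds no independent validation.

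The size of the loss depends on the true correlation. For r of about 0.2 to 0.4 the loss of power is material, most clearly at 0.30. From about 0.5 upward the cost is mainly an interval that is wider by about three quarters (0.37 against 0.21 at an observed 0.5). These figures rest on assumed correlations, unadjusted analysis, and Groups A and C together being the PTSD subjects. The documents do not support a claim that Hypothesis 1.2 as a whole is underpowered or bound to fail.

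**What to change.** In section 3.5, Hypothesis 1.2:

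1. State that the PTSD_sev marker from the preliminary study, specified before the database is analysed, is tested once, in a single regression of PCL-5 on PTSD_sev in all PTSD records (Groups A and C, with TBI status as a covariate). Report the correlation with its 95% confidence interval as the main result.
2. Keep the split only for the phase 2 analogue, in which PTSD_sev is re-selected in Subsamples 1 and 2 and tested in Subsample 3. State that the pooled result for the preliminary marker does not inform that re-selection.
3. State the significance level, the groups counted as PTSD subjects, the success criterion, and how the other health and quality-of-life measures are handled for multiplicity.

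The cost is a change of wording in the analysis plan. No new data, visits or recordings are needed.

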De-identification and Data Transfer to ENRM VA: The PSG recordings in the data repository, comprised of electrophysiological measures (such as EEG, EOG, EMG) will be exported to a binary format and will be completely stripped of any identification marks and will be saved with coded filenames. A separate text file containing epoch by epoch (30 second duration) sleep stages will be also generated for each sleep study with no patient's identification inside the file nor as part of the filename. Other de-identified data includes a spreadsheet with demographic information and survey data from Table 1. The de-identified data will be transferred from Portland VA to ENRM VA via a shared network folder with limited access permission.

**Prospective Study I.** The retrospective study of the existing database is from clinical sleep studies where 6 EEG electrodes, covering the occipital, central, and frontal lobes of the two hemispheres, were used. This is because all sleep states can be scored by these limited number of electrodes. However, using these 6 EEGs limits the coherence analysis to general areas of the frontal, central, and occipital lobes and with no direct representation for other areas of the brain. The aim of this prospective study is to evaluate potential improvement on the performance of the Neuromarkers using a dense array (up to 64 channels) EEG montage that covers all areas of the scalp. In the control and PTSD subjects, we will perform sleep studies using a dense array EEG montage and will compare the performance of the Neuromarkers in distinguishing PTSD from non-PTSD groups.

This entails starting with the coherence analysis based on the six electrodes used in the preliminary study followed by evaluating the nominal improvement in discrimination ability (PTSD vs. absence of PTSD) with the use of extra channels. The control subjects will be recruited by

advertising in the Bedford VA common areas, and by distributing informational flyers via VA providers, Veteran organizations, and other Veteran networks (including Veteran Services Offices, Veteran Centers, CBOC's, and other programs). We may also place an advertisement on Craigslist. Eligible Veterans will be able to self-refer to be screened for the study. The PTSD group will be recruited from Veterans undergoing treatment of PTSD at ENRM VA before the start of their treatment (Veterans with PTSD recruitment described in Section 4.2.3).

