Depending on the outcome of this study and the amount of potential improvements that might be achieved using a denser EEG arrays, we will identify the exact montage to be used in the follow-up prospective study with PTSD patients undergoing psychotherapy. We will thus start with the 6-channel EEG of the standard clinical sleep study, and potentially expand it by including more EEG locations to presumably produce results that are superior (more precise) to those obtained in preliminary studies

**Prospective Study II.** Up to sixty (60) Veterans with PTSD symptoms undergoing treatment at the ENRM VA will be recruited by the Research Coordinator. The study protocol will be explained to potential subjects which will be given ample time to consider their participation in the study and ask any questions they may have. They may take it home with them if they need more time and then return to the PTSD clinic. If the Veteran agrees to participate, they will sign all informed consent documents and be given a copy to retain. All protocols and informed consents related to this project will be approved by the ENRM VA Institutional Review Board (IRB).

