In the second phase of this hypothesis, the approach used to identify the most promising  $PTSD_{dx}$  neuromarker described in Preliminary Studies will be applied to the much larger dataset of 656 veterans. For this analysis, Subsamples 1 and 2 will serve as training (development) samples, and Subsample 3 will serve as the validation sample. For subsample 1, ANCOVA will again be used to identify the 5 most promising  $PTSD_{dx}$  neuromarkers (based on corresponding *F* and *p*-values) rank ordered across the 5 planned comparisons described above. This process will be repeated for Subsample 2. From these results, the most promising  $PTSD_{dx}$  neuromarker will be selected based on the lowest aggregate rank scores across both subsamples and across all 5 planned comparisons. Once this  $PTSD_{dx}$  neuromarker is identified, it will be formally tested using the 5 defined planned comparisons within Subsample 3, and again using a *p*-value of  $<0.01$  to define statistical significance. In aggregate, these analyses will determine whether the originally identified  $PTSD_{dx}$  neuromarker can discriminate between veterans with and without PTSD, and whether a potentially

more promising  $PTSD_{dx}$  neuromarker is identified.

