## **4.0 Human Subjects**

### **4.1 General Characteristics**

The project has three groups of human subjects’ involvement:

1. A retrospective study, where the analyses will be applied to a large existing database of health-related and functional outcome measures, as well as sleep EEG recordings. Database contains sleep EEG recordings from Veterans with PTSD only (n=107), with TBI only (n=126), with both PTSD and TBI (n=87), with depression only (n=80), and controls (no PTSD/TBI/Depression; n=256. The inclusion of records from TBI and depression only groups is to provide training data for the biomarker to become maximally sensitive and specific to PTSD in the presence of co-morbidities such as depression and TBI.
2. Prospective study 1 with up to 25 PTSD and control PTSD (n=10) and control (n=10) where we will evaluate potential improvement on the performance of the biomarkers using a dense array (up to 64 channel) EEG montage. For each participant, we will perform 2 sets of sleep studies that will be at least one week apart.
3. Prospective study 2 in a cohort (n=60) of Veterans undergoing psychotherapy, where we will evaluate the sensitivity of biomarkers to the improvements in PTSD symptoms, and other functional and HRQoL measures, in response to psychotherapy. These participants will undergo sleep studies at four times of time (a) Within one week before initiation of their treatment protocol; (b) Within one week after their first therapy session; (c) at the conclusion of their treatment phase; and (d) About three months after their last therapy sessions

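### The dense-array comparison selects, fits and scores extra electrodes in the same 20 to 25 subjects, so it will report an improvement even if the added channels are pure noise

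*Combined protocol and SAP*

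**What the plan says.** Section 3.5, Hypothesis 2, takes the marker developed under Hypothesis 1.1, which "will be prospectively evaluated in up to 25 PTSD and control subjects". Section 4.1 gives the split as 10 and 10. A standardized effect size (mean difference over SD) is computed for 6 channels. Next, "using forward stepwise linear regression, extra EEG electrodes whose addition increases the model coefficient of determination" by at least 1% are included. Once the final model is fitted, "the corresponding standardized effect size and 95% confidence interval will be calculated".

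The decision is numerical: "interpretation will not be based on formal statistical testing, but rather on the difference in the two effects sizes". The margin is 0.15, and the worked example requires 0.85 when the 6-channel value is 0.70.

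Section 3.3 (Prospective Study I) describes the task as "evaluating the nominal improvement in discrimination ability (PTSD vs. absence of PTSD) with the use of extra channels", with an array of up to 64 channels. It adds that, depending on the result, "we will identify the exact montage to be used in the follow-up prospective study with PTSD patients undergoing psychotherapy".

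Two other provisions might look like validation:

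- Under Hypothesis 1.1, "Subsamples 1 and 2 will serve as training (development) samples, and Subsample 3 will serve as the validation sample". That split covers the retrospective 6-channel recordings only.
- Section 4.1 states "For each participant, we will perform 2 sets of sleep studies that will be at least one week apart". The second recording is given no validation role.

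**The concern.** The same small group of subjects chooses the electrodes, sets their weights and supplies the effect size by which they are judged. Adding a regressor can never lower in-sample R-squared, and the effect size of a fitted two-group score is an increasing function of R-squared. The >6-channel figure is therefore biased upward by construction, while the 6-channel figure it is compared with is not inflated by any such search. With up to 58 extra channels and no more than 25 subjects, the search alone could be expected to exceed a 0.15 margin.

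This is the only analysis stated for Specific Aim 2. If it nearly always gives the same answer, the study cannot tell whether a dense array helps, and both a claim of better discrimination and an expanded montage would be unsupported. Hypothesis 3 is not shown to be affected, because its analysis uses the severity marker from Aim 1.

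**Working it through.** **Inputs.** From the plan: N = 25 (Section 3.5; taken here as 13 vs 12) or N = 20 (Section 4.1; 10 vs 10); 64 − 6 = 58 extra channels at most; entry threshold 0.01 in R²; margin 0.15; example effect 0.70. Assumed, because the plan does not say: group status is the dependent variable, each electrode contributes one Gaussian value, and the new effect size comes from the fitted score.

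**The plan's own figures.** Half the gap between adjacent categories is (0.5 − 0.2)/2 = (0.8 − 0.5)/2 = 0.15, and 0.70 + 0.15 = 0.85. Both reproduce. The plan gives no error rate for the rule.

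**How little is needed to pass.** For two groups, R² = d²/(d² + N(N−2)/(n1·n2)).

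- 13 vs 12: 25×23/156 = 3.686. R² is 0.49/4.176 = 0.117 at d = 0.70 and 0.7225/4.408 = 0.164 at d = 0.85. Gain needed: 0.047.
- 10 vs 10: 20×18/100 = 3.6. R² is 0.120 and 0.167. Gain needed: 0.047.

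**What one noise channel does.** Its share of the residual variance follows Beta(1/2, (N−3)/2). With a base R² of 0.109 (0.49/4.49), the 1% bar means a share of 0.01/0.891 = 0.0112. It is exceeded with probability 0.62 at N = 25 and 0.67 at N = 20. Passing the margin from exactly d = 0.70 needs a share of 0.0466/0.883 = 0.053 at N = 25, probability 0.28, or 0.0473/0.880 = 0.054 at N = 20, probability 0.34. With 58 independent noise channels, the chance that at least one passes alone is 1 − 0.72^58 at N = 25, which is 1 for practical purposes.

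**The full rule, simulated** (true 6-channel d = 0.70, no information in the extra channels, selection until the gain is below 1%, 4,000 runs per setting, both sample sizes):

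| Candidates offered | Improvement declared |
|---|---|
| 58 or 20 | 100% |
| 8 | 99-100% |
| 5 | 92-97% |
| 3 | 75-83% |
| 1 | 31-38% |

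Independent re-runs agree to within a few points; the single-candidate figure ranged from 30% to 42%. With 58 candidates the median effect size rose from 0.72 to 12.9 at N = 25 (11 channels added) and from 0.73 to 15.2 at N = 20 (9 added). The rate stayed at 100% for true d from 0 to 1.5, with the six channels entered separately, and with 25 vs 25 subjects.

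**Sensitivity.**

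- Correlation between an extra channel and the marker makes no difference here, because the marker is already in the model.
- Shared structure among the extra channels does matter, but less than one might hope: 97% at a mutual correlation of 0.95, and 79% and 95% when three or five exact common factors generate all 58 channels (13 vs 12).
- If selected channels are averaged with the marker at equal weight instead (58 candidates), the rate is 85-97% at correlation 0 to 0.5 with the marker and 19-28% at 0.9 when signs are aligned in-sample. Without alignment it is 4-24%.
- Selecting on the first recording and scoring the second in the same people (58 candidates, both recordings dense-array) still gives 51-53% at an assumed between-night ICC of 0.5 and 94% at 0.8.
- With no selection at all, two equally good scores correlated 0.8 to 0.95 in 25 subjects differ by at least 0.15 in favour of the dense score in 14-30% of runs (SD of the difference 0.15 to 0.29).

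**The case against.** The strongest reply is that this is a declared pilot. The plan disclaims formal testing, speaks of nominal improvement, and treats a gain as only a potential indication for more complex testing. The follow-up study uses the same 64-channel device and builds on the 6 channels, so an unjustified expansion loses no 6-channel data, and Hypothesis 3 is not shown to suffer. The 100% figure also rests on one reading of an underspecified procedure.

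Part of this stands. The downstream harm is confined to an unsupported montage choice and an unsupported claim. The headline rate is conditional: averaging channels without sign alignment would bring it down to 4-24%, and few or strongly redundant candidates would also lower it.

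The rest does not. The fault is bias, and calling the study a pilot does not remove bias from a numerical rule that the plan uses to choose a montage. The planned confidence intervals do not help either: the decision uses the difference in point estimates, and an ordinary interval around a selected model ignores the selection. Under-specification is itself a reason to amend the text before analysis.

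**Conclusion.** The concern holds, and the rule is wrong as written. With the full array offered and the score taken from the fitted model, it declares improvement in about 100% of runs when the extra channels carry nothing. The rate falls clearly below 90% only with about four or fewer independent candidates, with channels generated by very few common factors, or under some versions of equal-weight averaging. The conclusion assumes group status as the outcome, one Gaussian value per electrode and no group information in the extra channels beyond the marker. Offering pairwise coherence values instead would add candidates and increase the optimism. The analysis should be changed before any Study 2 data are analysed.

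**What to change.** Do not base the 0.15 decision on the in-sample effect size. Instead:

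1. State the dependent variable and how an electrode enters the score. Name a small candidate set (for example, at most 8 scalp regions) and cap additions (for example, 2).
2. Repeat the whole capped selection inside each leave-one-subject-out fold, leaving out both recordings of a participant together. Compute the >6-channel effect size from held-out scores, and report its difference from the 6-channel value with a paired bootstrap interval.
3. Build a permutation reference for the R² gain under the same cap: residualise the extra channels on the 6-channel score, shuffle rows across subjects, and re-run the selection.
4. Call it an improvement only if the held-out difference is at least 0.15 and the permutation p is at most 0.05.
5. Check the rule's false-positive rate and power by simulation beforehand, and label the result exploratory.

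Both conditions are worth keeping. With 8 candidates and a cap of 2, pure noise passes the held-out margin alone in 15-20% of runs, the permutation test alone in 4-6%, and both in 4-5%. The held-out estimate supplies an honest size; the permutation test supplies most of the error control.

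The cost is SAP wording and computing, with no new data, but power is limited. If one extra channel carries an independent d of 1.5 (combined √(0.49 + 2.25) = 1.66), the rule detects it in 56% of runs at 13 vs 12 and 42% at 10 vs 10. For d = 1.0 (combined √(0.49 + 1) = 1.22) the figures are 25% and 17%. Offering all 58 candidates under the same cap lowers the d = 1.5 figures to 36% and 23%. Without a cap the combined rule detected almost nothing (0-1% of 100 runs at 13 vs 12). A negative result would therefore not show that the extra channels are uninformative.

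If the team prefers no test in a pilot, the simpler course is to drop the 0.15 declaration, report the held-out estimates with their interval, and set the follow-up montage independently of this comparison.
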